6.3.1.2 Radiotherapy

An overview of the RT technique (intensity-modulated radiotherapy [IMRT]) for dose escalation Arm B (SCCHN) in Phase Ia and both expansion cohorts in Phase Ib is given in [Appendix D](#).

6.3.2 Ancillary cPoP Part

Subjects will receive a single high dose of RT (10-25 Gy) given on Lesion 1 on Day 1. On Day 2, subjects will receive a single dose of M3814 in combination with a single high dose of RT (10-25 Gy) given on Lesion 2. Subjects will fast for 1.5 hours prior to dose administration and continue to fast for 1 hour postdose. M3814 will be administered 1.5 hour (± 30 minutes) before the start of RT.

The dose of M3814 to be administered to subjects in successive cohorts of the ancillary cPoP part of the trial is shown in [Table 12](#).

6.4 Assignment to Treatment Groups

All eligible subjects will be assigned to receive open label M3814. Subjects will be assigned to treatment sequentially. During dose escalation (Phase Ia) and for the first 3 NSCLC subjects in the Arm A expansion cohort (Phase Ib), the next dose level will be open for enrollment only after the DLTs in the current dose level have been fully evaluated by the SMC and a formal SMC decision to proceed to the next dose level has been documented.

6.5 Noninvestigational Medicinal Products to be Used

Not applicable.

6.6 Concomitant Medications and Therapies

All concomitant medications taken by the subject during the trial, from the date of signature of informed consent are to be recorded in the appropriate section of the eCRF, noting the name, dose, duration and indication of each drug. Nondrug interventions and any changes to a concomitant medication or other intervention should also be recorded in the eCRF.

6.6.1 Permitted Medicines

Any medications (other than those excluded by the clinical trial protocol) that are considered necessary for the subjects' welfare and will not interfere with the trial medication may be given at the Investigator's discretion.

The following medications are permitted:

- Local, topical, or short-term (i.e., <7 days) of systemic corticosteroids
- Anti-infectious drugs
- Hematopoietic growth factors, if medically indicated.

The Investigator will record all concomitant medications taken by the subject and any concomitant procedures provided to the subject during the trial, from the date of signature of informed consent, in the appropriate sections of the eCRF.

Any additional concomitant therapy that becomes necessary during the trial and any change to concomitant drugs must be recorded in the corresponding section of the eCRF, noting the name, dose, duration and indication of each drug.

6.6.2 Prohibited Medicines

As stated in Section [5.3.2](#), subjects must not have received chemotherapy, immunotherapy, hormonal therapy, biologic therapy, or any other anticancer therapy or any investigational agent

within 28 days of the first dose of IMP administration (6 weeks for nitrosoureas or mitomycin C), except for subjects with rapidly growing tumors localized in the head and neck region or thorax where the treating physician cannot wait for 28 days. These therapies are also prohibited during the treatment period and up to 30 days after RT, with the exception of concurrent cisplatin in the SCCHN population (Arm B). During the treatment period and up to 30 days after RT, any other investigational agent, chemotherapy, extensive RT (involving $\geq 30\%$ of bone marrow) or any other anticancer therapy (biologics or other targeted therapy) and antineoplastic steroid therapy are also prohibited (Phase Ia and Phase Ib only). Use of any investigational agent during the entire trial duration is not permitted.

Medications or herbal supplements known to be potent inhibitors or inducers of CYP3A or CYP2C19, or drugs mainly metabolized by CYP3A with a narrow therapeutic index as judged by the Investigator (and after optional consultation with the Sponsor) are prohibited (see Section 6.6.4 for details).

The solubility of M3814 is pH dependent; therefore, antacid drugs, H₂-blocker and PPIs might affect absorption. H₂-blockers or PPIs should be stopped 5 days prior to the first treatment, and avoided during the entire treatment period with IMP. Antacid drugs should not be taken 1 hour before IMP administration until 2 hours after IMP administration.

If the administration of a nonpermitted concomitant drug becomes necessary during the treatment period, e.g., due to AEs, the subject should be discontinued from the trial treatment and complete all assessments listed under the ETT visit.

See also Section 6.6.4 for details of possible drug-drug interactions with and by concomitant medication.

6.6.3 Other Interventions

The planning of RT will be in accordance with local practice.

Phase Ia: subjects will receive fractionated palliative RT (Arm A; 3 Gy x 10, 5 F/W) or fractionated RT (Arm B; 2 Gy x 33 to 35, 5 F/W) as part of curatively intended CRT (with concurrent cisplatin).

Phase Ib: NSCLC subjects will receive fractionated RT (2 Gy x 33, 5 F/W); SCCHN subjects will receive the same CRT regimen as in Phase Ia.

[figure not shown]
Missed fraction(s) of RT must be given at the end of the schedule to ensure that the total dose is reached. The dose of M3814 should be administered 1.5 hours (\pm 30 minutes) before RT. Where applicable, cisplatin should be administered according to institutional guidelines (see Section 6.3.1.1).

Ancillary cPoP part: subjects will receive a single high dose of RT (10-25 Gy) on Day 1 given on Lesion 1 and a single high dose of RT (10-25 Gy) on Day 2 given on Lesion 2.

6.6.3.1 Radiotherapy Treatment Delay

The formal criteria for modification of RT treatment are presented in [Table 13](#). Within this trial, a maximum delay of up to and including 7 days in total is allowed within the complete treatment period. If RT and IMP treatment have to be delayed by more than 7 days, the subject must be discontinued from IMP.

CCI

6.6.5 Management of Specific Adverse Events or Adverse Drug Reactions

At the current stage of development there are no known ADRs or specific AEs.

Early and late toxicities related to RT and/or M3814 will be managed according to the local institute's guidelines.

Overdose of cisplatin generally results in severe forms of normally occurring adverse reactions. Investigators are asked to check the respective information in the SmPC for further advice.

6.7 Packaging and Labeling of the Investigational Medicinal Product

M3814 will be packaged as boxes of CCI packs of 10 mg, 50 mg or 100 mg capsules or 50 mg tablets.

Packaging and labeling will be in accordance with all applicable local regulatory requirements and applicable Good Manufacturing Practice Guidelines.

6.8 Preparation, Handling, and Storage of the Investigational Medicinal Product

M3814 should be stored at the recommended temperature CCI. Any deviations from the recommended storage conditions should be immediately reported to the contact specified in the Manual of Operations, and the trial drug should not be used until authorization has been received from the Sponsor or CRO.

The Investigator or a trained designee will dispense M3814 to subjects according to their allocated dose level.

Cisplatin will be stored according to the package insert and the SmPC.

6.9 Investigational Medicinal Product Accountability

The Investigator is responsible for ensuring accountability for M3814, including reconciliation of drugs and maintenance of records.

- Upon receipt of M3814, the responsible person will check for accurate delivery and acknowledge receipt by signing or initialing and dating the appropriate documentation provided by the Sponsor/CRO and returning it to the location specified. A copy will be archived for the Investigator Site File.
- IMP dispensing will be recorded on the appropriate drug accountability forms provided by the Sponsor/CRO so that accurate records will be available for verification at each monitoring visit.
- Trial site IMP accountability records will include the following:
 - Confirmation of IMP receipt, in good condition and in the defined temperature range
 - The inventory of IMP provided for the clinical trial and prepared at the site
 - The use of each dose by each subject
 - The disposition (including return, if applicable) of any unused IMP
 - Dates, quantities, batch numbers, vial numbers, expiry dates, formulation (for IMP prepared at the site), and the individual subject trial numbers.

The Investigator site should maintain records, which adequately document that subjects were provided the doses specified in this protocol, and that all IMPs provided were fully reconciled.

Unused IMP must not be discarded or used for any purpose other than the present trial. Any IMP that has been dispensed to a subject must not be redispensed to a different subject.

The Sponsor Monitor will periodically collect the IMP accountability forms and will check all returns (both unused and used containers) before authorizing their destruction by the trial site.

6.10 Assessment of Investigational Medicinal Product Compliance

M3814 will be administered at the site by the Investigator or designated personnel. M3814 administration, including batch numbers, kit numbers, and vial numbers must be recorded in the eCRF, as applicable.

Drug administration records will be used to assess compliance.

The Investigator is responsible for the control of drugs under investigation; adequate records of the receipt (e.g., Drug Receipt Record) and disposition (e.g., Drug Accountability Record, Drug Destruction Record) of the IMP, including dates, quantities, and use by subject, must be maintained.

All records and drug supplies must be available for inspection at every monitoring visit. Once the trial has been terminated and drug accountability has been satisfactorily completed by the pharmacist or trial drug preparer (or designee), the used and unused IMP (i.e., empty, partially used, and unused containers) will be released for local destruction following the internal standard operating procedures of the designated facility. The completed Drug Accountability and Drug Destruction Records will be sent to the monitor or its designee.

The site pharmacist or trial drug preparer (or designee) must maintain records of the delivery of the IMP to the trial site, the inventory at the site, the use by each subject and IMP destruction at the clinical site after drug accountability has been performed by the responsible monitor. The drug-dispensing log must be kept current, listing the identification of the subject who received IMP along with the date and quantity of IMP dispensed; it must be available for monitoring. Records shall also be maintained by the Investigator of the method of destruction (taking into account the requirements of local law), and the person who disposed of the trial drug. The temperature of the storage facilities will be monitored and documented.

After completion of the trial, any IMP distributed to the site but not administered or dispensed to or taken by the subject will be destroyed at the site. All unused medications will be carefully recorded and documented before destruction. The Investigator will ensure that the trial drug supply is not used for any purpose other than the current trial.

6.11 Blinding

This is an open label trial; therefore, no blinding will be performed.

6.12 Emergency Unblinding

Not applicable.

6.13 Treatment of Overdose

An overdose is defined as any dose greater than the highest daily dose included in a clinical trial protocol or planned for an individual subject enrolled in the trial. Even if it does not meet other criteria for an SAE, any overdose must be recorded in the trial medication section of the eCRF and reported to Drug Safety in an expedited manner using the SAE Report Form, and following the procedure in Section [7.4.1.4](#).

There is no established treatment for overdose with M3814. The Investigator should use clinical judgment to manage any overdose considering the presenting symptoms and standard evaluation results.

6.14 Medical Care of Subjects after End of Trial

After a subject has completed the trial or has withdrawn early, usual treatment will be administered, if required, in accordance with the trial site's SoC and generally accepted medical practice and depending on the subject's individual medical needs.

7 Trial Procedures and Assessments

7.1 Schedule of Assessments

Prior to performing any trial assessments that are not part of routine medical care for the subject, the Investigator will obtain written informed consent as described in Section [9.2](#).

Complete schedules of assessments for Phase Ia (Arm A – Capsule and Tablet), Phase Ib – first 3 subjects (Arm A, NSCLC cohort), Phase Ib (Arm A, NSCLC cohort), Phase Ia (Arm B, SCCHN cohort), Phase Ib (Arm B, SCCHN cohort) and ancillary cPoP parts are provided in [Table 1](#), [Table 2](#), [Table 3](#), [Table 4](#), [Table 5](#), [Table 6](#) and [Table 7](#), respectively. During RT, no visit window will be allowed.

Every effort should be made to perform assessments as close as possible to the scheduled time points.

7.1.1 Screening Period (Day -21 to Day -1)

Based on the findings obtained during the Screening Period, the Investigator will decide whether the subject is eligible for the trial. Scheduled screening assessments in all subjects are as follows:

- Provision of written informed consent for the trial and PGx analysis and review of inclusion and exclusion criteria
- Documentation of demographics, relevant medical history, and concomitant medications

- Safety laboratory (hematology, serum chemistry, urinalysis, coagulation and serum β -human chorionic gonadotropin [HCG] pregnancy test [if applicable])
- Infection screen. Hepatitis B and C testing to be performed unless obtained within 3 months prior to Screening. Screening for HIV will be performed according to local practice and local regulatory guidance
- Evaluation of human papillomavirus status in tumor material by immunohistochemistry (Phase Ia, Arm B and Phase Ib, Arm B expansion cohort only)
- Audiogram, as needed according to local guidelines (Phase Ia, Arm B and Phase Ib, Arm B expansion cohort only)
- Assessment of vital signs (blood pressure and heart rate), body weight, and height, body temperature (height measured at Screening only)
- Assessment of AEs
- Tumor evaluation by radiographic or other modality (RECIST v1.1) (Phase Ia and Phase Ib only). Baseline tumor evaluation can be up to 28 days old when treatment starts
- ECOG PS
- 12-lead ECG including the Fridericia-corrected QT interval (QTcF)
- Physical examination
- Clinical examination of bleeding (including petechiae, in skin, in the sclera of the eye, oral mucosa) (Phase Ia and Phase Ib only).
- In case of clinical signs of esophagitis, an esophageal endoscopy must be performed, if the radiation fields involve the esophagus.

Ancillary cPoP part of the trial only:

- Evaluation of all tissues in the RT area
- Local tumor assessment (in irradiated lesions) by clinical exam or imaging according to RECIST v1.1 (only applicable for additional cohorts of M3814 [CC1 formulation]).

7.1.2 Treatment Period

7.1.2.1 Phase Ia Part: Arm A and Arm B (Fraction Days 1 to 10)

Eligible subjects will receive M3814 during the period in which RT is given.

The following assessments will be performed on Fraction Days 1, 6 and 10; if Fraction Day 10 is on a Friday, PK, CC1 safety laboratory, and urinalysis sampling must be done on Fraction Day 9:

- Review of inclusion and exclusion criteria (Fraction Day 1 only)
- Assessment of vital signs (blood pressure, heart rate, and body temperature), body weight (see Section 7.4.4 for details)

- Physical examination
- Clinical examination of bleeding (including petechiae, in skin, in the sclera of the eye, oral mucosa)
- Evaluation of all tissues in the RT area (Fraction Day 6 and 10 only)
- ECOG PS (Fraction Day 10 only)
- Assessment of AEs
- Documentation of concomitant medications
- Safety laboratory (hematology, serum chemistry and coagulation)
- Urinalysis (Fraction Day 10 only)
- 12-lead ECG including QTcF (Fraction Day 1 and 10)
- Collection of PK blood samples
- Availability of archival tumor material, either as a block or slides. If no archival material is available then a fresh biopsy should be taken

CCI

The following assessments will be performed on Fraction Day 2:

- Collection of PK blood samples (predose)

CCI

7.1.2.2 Phase Ia Part: Arm B (SCCHN) (Fraction Days 16 to 31)

Eligible subjects will receive M3814 during the period in which RT is given.

The following assessments will be performed on Fraction Days 16, 21, 26, 31, and last FD/ETT

- Assessment of vital signs (blood pressure, heart rate, and body temperature), body weight (see Section [7.4.4](#) for details)
- Physical examination
- Clinical examination of bleeding (including petechiae, in skin, in the sclera of the eye, oral mucosa)
- Evaluation of all tissues in the RT area
- ECOG PS (last Fraction Day only)
- Assessment of AEs
- Documentation of concomitant medications

- Safety laboratory (hematology, serum chemistry and coagulation)
- Urinalysis (Fraction Day 16 and last Fraction Day only)
- 12-lead ECG including QTcF

[figure not shown]
7.1.2.3 Phase Ib Part: Arm A (NSCLC) Expansion Cohort (Fraction Days 1 to 33)

Eligible subjects will receive M3814 during the period in which RT is given.

The following assessments will be performed on Fraction Days 1, 6 (first 3 subjects only), 10, 16, 21, 26 and 33; if Fraction Day 10 is on a Friday, PK, PD, and safety laboratory sampling must be done on Fraction Day 9:

- Review of inclusion and exclusion criteria (Fraction Day 1 only)
- Assessment of vital signs (blood pressure, heart rate, and body temperature), body weight (see Section [7.4.4](#) for details)
- Physical examination
- Clinical examination of bleeding (including petechiae, in skin, in the sclera of the eye, oral mucosa)
- Evaluation of all tissues in the RT area (not performed on Fraction Day 1)
- ECOG PS (Fraction Day 33 only)
- Assessment of AEs
- Documentation of concomitant medications
- Safety laboratory (hematology, serum chemistry and coagulation)
- Urinalysis (Fraction Days 10 [first 3 subjects only], 16, and 33 only)
- 12-lead ECG including QTcF (Fraction Day 1 and 10)
- Collection of PK blood samples (Fraction Days 1 and 10 only)
- Availability of archival tumor material, either as a block or slides. If no archival material is available then a fresh biopsy should be taken

CCI

The following assignments will be performed on Fraction Day 2 (first 3 subjects only):

- Collection of PK blood samples (predose)

CCI

7.1.2.4 Phase Ib Part: Arm B (SCCHN) Expansion Cohort (Fraction Days 1 to Last Fraction Day)

Eligible subjects will receive M3814 during the period in which CRT is given.

The following assessments will be performed on Fraction Days 1, 6, 10, 16, 21, 26, 31 and the last Fraction Day (33 to 35); if Fraction Day 10 is on a Friday, PK, **CCI** and safety laboratory sampling must be done on Fraction Day 9:

- Review of inclusion and exclusion criteria (Fraction Day 1 only)
- Assessment of vital signs (blood pressure, heart rate, and body temperature), body weight (see Section [7.4.4](#) for details)
- Physical examination
- Clinical examination of bleeding (including petechiae, in skin, in the sclera of the eye, oral mucosa)
- Evaluation of all tissues in the RT area (not performed on Fraction Day 1)
- ECOG PS (last Fraction Day only)
- Assessment of AEs
- Documentation of concomitant medications
- Safety laboratory (hematology, serum chemistry and coagulation)
- Urinalysis (Fraction Day 16 and last Fraction Day only)
- 12-lead ECG including QTcF
- Collection of PK blood samples (Fraction Days 1 and 10 only)
- Availability of archival tumor material, either as a block or slides. If no archival material is available then a fresh biopsy should be taken

CCI

7.1.2.5 Ancillary cPoP Part

Eligible subjects will receive a single high dose of RT given on Lesion 1 on Day 1, and on Day 2, will receive M3814 with a single high dose of RT given on Lesion 2.

[figure not shown]
For logistical reasons (handling and sending materials), Day 1 must be on a Wednesday or earlier.

The following assessments will be performed on Day 1 and Day 2:

- Assessment of vital signs (blood pressure, heart rate, and body temperature), body weight (see Section [7.4.4](#) for details).

- Evaluation of all tissues in the RT area (Day 2 only)
- Assessment of AEs
- Documentation of concomitant medications
- Tumor biopsy:
 - Day 1: baseline biopsy to be taken any time prior to RT for both lesions (Screening to Day 1) and 2-4 hours after RT for Lesion 1
 - Day 2: to be taken 2-4 hours after RT for Lesion 2.

CCI

7.1.3 Follow-up Period

7.1.3.1 DLT Period: Phase Ia, Arm A

The following assessments will be performed on PTD 8 and 15:

- Assessment of vital signs (blood pressure, heart rate, and body temperature), body weight
- Physical examination
- Clinical examination of bleeding (including petechiae, in skin, in the sclera of the eye, oral mucosa)
- Evaluation of all tissues in the RT area
- ECOG PS
- Assessment of AEs
- Documentation of concomitant medications
- Safety laboratory (hematology, serum chemistry and coagulation)
- Urinalysis.

7.1.3.2 DLT Period/Short-term Safety Follow-up: Phase Ia, Arm B and First 3 Subjects in Phase Ib (Arm A Expansion Cohort in NSCLC)

The following assessments will be performed on PTD 7, 14, 21, 28 and 35 (Phase Ia, Arm B) or on PTD 8, 15, 22 and 37 (first 3 subjects in Phase Ib, Arm A):

- Serum β -HCG pregnancy test (if applicable and only PTD 28 [Phase Ia, Arm B] or PTD 22 [first 3 subjects in Phase Ib, Arm A])
- Assessment of vital signs (blood pressure, heart rate, and body temperature), body weight
- Physical examination
- Clinical examination of bleeding (including petechiae, in skin, in the sclera of the eye, oral mucosa)
- Evaluation of all tissues in the RT area
- ECOG PS
- Assessment of AEs
- Documentation of concomitant medications
- Safety laboratory (hematology, serum chemistry and coagulation)
- Urinalysis.

7.1.3.3 Short-term Safety Follow-up: Phase Ia, Arm A and Phase Ib

The following assessments will be performed on PTD 22 and 30 in Phase Ia (Arm A) and on PTD 8, 15, 22 and 30 in Phase Ib:

- Serum β -HCG pregnancy test (if applicable and only PTD 30)
- Assessment of vital signs (blood pressure, heart rate, and body temperature), body weight
- Physical examination
- Clinical examination of bleeding (including petechiae, in skin, in the sclera of the eye, oral mucosa)
- Evaluation of all tissues in the RT area
- ECOG PS (PTD 30 only)
- Assessment of AEs
- Documentation of concomitant medications
- Safety laboratory (hematology, serum chemistry and coagulation)
- Urinalysis (PTD 30 only).

7.1.3.4 Mid-term Safety Follow-up: Phase Ia and Phase Ib

The mid-term safety follow-up will be performed on PTD 84. To evaluate signs of RT-induced toxicity on normal surrounding tissues, the following assessments were performed:

- Assessment of vital signs (blood pressure, heart rate, and body temperature), body weight (Phase Ia only)
- Physical examination
- 12-lead ECG including QTcF (Arm B SCCHN cohort only)
- ECOG PS
- Evaluation of all tissues in the RT area
- Evaluation of ongoing TEAEs

7.1.3.5 Long-term Safety Follow-up: Phase Ia and Phase Ib

The following assessments will be performed for all subjects, excluding subjects in the ancillary cPoP part of the trial, on PTD 42, 126, 168, and 180, (Phase Ia and Phase Ib), and on PTD 270 and 365 (Phase Ib only):

- Assessment of vital signs (blood pressure, heart rate, and body temperature), body weight
- Physical examination
- 12-lead ECG including QTcF (Arm B SCCHN cohort only)
- ECOG PS
- Evaluation of all tissues in the RT area
- Evaluation of ongoing TEAEs
- Tumor assessment according to RECIST v1.1, only required if subject has not started a new antitumor treatment. If a new treatment is started, the date (and regimen) must be reported in eCRF.

The following assessments will be performed on PTD 210 and 312:

- Evaluation of long term RT toxicity (subject called by phone).

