- a. All subjects will be followed up for response until 12 months after the last subject has stopped RT/CRT, or earlier due to any reason whereby tumor assessments are no longer applicable (e.g., if a new treatment is started, withdrawal of consent). The reason for early discontinuation should be captured in the source document. If EOT occurs before PTD 365, all assessments must be done as planned for PTD 365. After completing the PTD 365 visit, subjects will be followed up for survival via phone call every 3 months, wherever possible.
- b. RT to be given 1.5 hours (\pm 30 minutes) after dosing.
- c. FD10 is the day of the last dose of RT. In case of premature withdrawal from the trial during the treatment period, the investigations scheduled for the visit on FD10 should be performed. In such cases this visit will be considered the Early Treatment Termination visit. If FD10 is on a Friday, PK, PD, safety laboratory, and urinalysis sampling must be done on FD9.
- d. All AEs will be collected from FD1 up to PTD 21 to evaluate the occurrence of DLTs.
- e. Hepatitis B and C testing to be performed at Screening unless obtained within 3 months prior to Screening. Screening for HIV will be performed according to local practice and local regulatory guidance.
- f. Heart rate, diastolic and systolic blood pressure, body temperature, and body weight. See Section [7.4.4](#) for details.
- g. Height measured at Screening only.
- h. Only required if subject has not started a new antitumor treatment. If a new treatment is started, the date (and regimen) must be reported in the eCRF.
- i. Physical exam will report findings in the irradiated area during all FU periods.
- j. Evaluation of ongoing treatment-emergent adverse events.
- k. See [Table 15](#) for details of hematology tests.
- l. See [Table 15](#) for details of serum chemistry tests.
- m. Urinalysis: dipstick followed by microscopic examination if abnormal results.
- n. 12-lead resting ECG in triplicate.
- o. 12-lead ECG to be performed predose and once at 2 to 3 hours postdose.
- p. 12-lead ECG to be performed at 2 hours postdose.
- q. Tumor imaging by CT or MRI at baseline to document extent of lesions according to RECIST v1.1. Baseline tumor evaluation can be up to 28 days old when treatment starts.

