- r. Tumor assessments to be done at long-term safety FU (every 6 weeks during Day 31-180 [4 assessments]) and during survival FU (every 13 weeks during Day 181-365 [2 assessments]). Tumor assessment will not be repeated on PTD 180.
- s. PK samples will be collected as detailed in [Table 9](#). Sampling schedule may be changed by the SMC based on emerging data. See Section [7.5.1](#) for details.
- t. Predose only.
- u. Mandatory archival tumor materials sampled before start of the treatment (most recent materials available). If no archival tumor material is available a fresh biopsy must be taken.

CCI

- x. PTD 210 and 312 will consist of phone calls to evaluate long term RT toxicity. No other assessments will be performed at these visits.
- y. Can be followed up via phone call every 3 months.

Table 2 Schedule of Assessments – Phase Ia (Arm A): Tablet Cohorts

Trial Periods	Screening	DLT Evaluation Period					Short-term Safety FU	Mid-term Safety FU	Long-term Safety FU	Survival FU/EOT ^a
		Treatment Period (M3814 + RT)			DLT Period					
Trial Days	Day -21 to Day -1	FD 1 to FD 10			PTD 1 to 21	PTD 22 to 30	PTD 1 to 90	PTD 31 to 365	PTD 181 to 365	
M3814 Tablet ^y	-	X		X						-
M3814 Capsule			X							
RT 3 Gy x 10 (5 F/W) ^b	-	X								-
Visit Days	-21 to -1	FD1	FD2	FD6 ^z	FD7	FD10 ^c /ETT	PTD 8, 15	PTD 22 ^d , 30	PTD 84	PTD 42, 126, 168, 180, 210 ^{aa} , and 312 ^{aa}
Visit Window (days)	-	-		-		-	±2	±2	±7	±7
Signed informed consent	X									
Inclusion/exclusion criteria	X	X								
Demography	X									
Medical history	X									
Serum β-HCG pregnancy test (if applicable)	X						PTD 30 only			
Infection screen (hepatitis B and C), optional HIV test ^e	X									
Vital signs ^f	X ^g	X		X		X	X	X	X	X ^h
Physical examination	X	X		X		X	X	X	X	X ⁱ
Clinical examination of bleeding	X	X		X		X	X			

Trial Periods	Screening	DLT Evaluation Period					Short-term Safety FU	Mid-term Safety FU	Long-term Safety FU	Survival FU/EOT ^a
		Treatment Period (M3814 + RT)			DLT Period					
Trial Days	Day -21 to Day -1	FD 1 to FD 10			PTD 1 to 21	PTD 22 to 30	PTD 1 to 90	PTD 31 to 365	PTD 181 to 365	
M3814 Tablet ^y	-	X		X						-
M3814 Capsule			X							
RT 3 Gy x 10 (5 F/W) ^b	-	X								-
Visit Days	-21 to -1	FD1	FD2	FD6 ^z	FD7	FD10 ^c / ETT	PTD 8, 15	PTD 22 ^d , 30	PTD 84	PTD 42, 126, 168, 180, 210 ^{aa} , and 312 ^{aa}
Visit Window (days)	-	-		-		-	±2	±2	±7	±7
Esophageal endoscopy (if relevant)	X									
Evaluation of all tissues in RT area				X		X	X	X	X	X

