7.4.1.3 Definition of the Adverse Event Reporting Period

The AE reporting period for safety surveillance begins when the subject is initially included in the trial (date of first signature of informed consent) and continues through the trial's post-treatment follow-up period up to PTD 365.

A TEAE is defined as any AE that occurs from the day of first dose of M3814 (regardless of pretreatment or post-treatment on first dosing day), through Day 30 after the end of RT.

Any SAE assessed as related to M3814 must be reported whenever it occurs irrespective of the time elapsed since the last administration of M3814.

7.4.1.4 Procedure for Reporting Serious Adverse Events, Adverse Events of Special Interest and Dose Limiting Toxicities

Serious Adverse Events

In the event of any new SAE occurring during the reporting period, the Investigator must immediately (within a maximum of 24 hours after becoming aware of the event) inform the Sponsor or its designee in writing. All written reports should be transmitted using the SAE Report Form, which must be completed by the Investigator following specific completion instructions.

In exceptional circumstances, an SAE (or follow-up information) may be reported by telephone; in these cases, a written report must be sent immediately thereafter.

Relevant pages from the eCRF may be provided in parallel (e.g., medical history, concomitant medication). Additional documents may be provided by the Investigator, if available (for example, laboratory results, hospital report and autopsy report). In all cases, the information provided on the SAE Report Form must be consistent with the data about the event recorded in the eCRF.

The Investigator must respond to any request for follow-up information (e.g., additional information, outcome, final evaluation, other records where needed) or to any question the Sponsor/designee may have on the AE within the same timelines as those noted above for initial reports. This is necessary to ensure prompt assessment of the event by the Sponsor or designee and (as applicable) to allow the Sponsor to meet strict regulatory timelines associated with expedited safety reporting obligations.

Requests for follow-up will usually be made via the responsible Monitor, although in exceptional circumstances the CRO's Global Drug Safety department may contact the Investigator directly to obtain further information or to discuss the event.

Dose Limiting Toxicities

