15.2.3 Late toxicities

A number of outputs will be produced for late adverse events. An adverse event is defined as late if it starts after the on-treatment period and it meets one of the following criteria:

- It is the first occurrence of adverse event for this participant on MedDRA preferred term level
- It is a recurring adverse event but there is gap between the end date of the previous occurrence and the start date of the re-occurrence (start date of reoccurrence – end date of previous occurrence > 0)
- It is a reccuring adverse event without gap between the end date of the previous occurrence and the start date of the re-occurrence and the grade has worsened:

The following will be produced for late toxicities:

- Table of all late toxicities by worst CTCAE grades: any grade (including AEs with missing grade), grades ≥ 3 , ≥ 4 and 5
- Listing of all late toxicities related to M3814
- Listing of all late toxicities related to radiotherapy
- Listing of all late toxicities grade ≥ 3

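### The AE line at the seven clinic visits from PTD 42 to PTD 365 names only ongoing TEAEs, which conflicts with the protocol's own rule to record new AEs up to PTD 365

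*Protocol*

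**What the plan says.** **Visit lists.** Protocol 7.1.3.4 (PTD 84), 7.1.3.5 (PTD 42, 126, 168 and 180 in both phases; PTD 270 and 365 in Phase Ib) and 7.1.3.6 (PTD 270 and 365 in Phase Ia Arm A) each give the AE task as "Evaluation of ongoing TEAEs". The AE footnotes for the follow-up columns read "Evaluation of ongoing treatment-emergent adverse events" in all six schedules for the core trial (Tables 1 to 6).

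**Other content of follow-up.** The same seven visits also require a physical examination and "Evaluation of all tissues in the RT area". Two further contacts are by telephone: "PTD 210 and 312 will consist of phone calls to evaluate long term RT toxicity".

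**General AE rules.** Section 7.4.1.2 has the subject asked about changes at each trial visit, with any unfavourable change in the reporting period recorded as an AE. Section 7.4.1.3 runs that period through the "post-treatment follow-up period up to PTD 365". It also closes the TEAE window at Day 30 after the end of RT.

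**SAP.** Section 15.2.3 states: "An adverse event is defined as late if it starts after the on-treatment period". It then requires one of three things: a first occurrence, a recurrence after a gap, or a recurrence without a gap at a worse grade. This SAP covers Phase Ia; Phase Ib has its own plan.

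**The concern.** The phrase in the visit lists is a defined term with a closing date, and these visits all fall after that date. Read as written, the line tells the site to follow events already on record and does not mention new ones. The wording also changes between visit types. In 7.1.3.1 to 7.1.3.3 the line is a general assessment of AEs; from the mid-term visit on it becomes ongoing TEAEs. A site could reasonably take that as a deliberate narrowing.

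Late toxicity is a stated reason for this follow-up. Section 3.6 describes RT effects that arise three months or later after RT and says they may be more severe with M3814. Section 5.1.1 says the 3-month follow-up data, once available, will guide escalation and the RP2D. Section 7.4.1.5 lets the SMC declare late in-field radiation toxicities as DLTs. If the visit line were followed literally, the error would run one way, because new late events would be missed and none would be added.

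**Working it through.** No power or sample-size arithmetic applies. The check compares the definitions and counts the contacts.

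**1. Contacts common to Phase Ia and Ib from PTD 42 on**

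| Contact | Where specified | AE task stated | RT-area tissue evaluation |
|---|---|---|---|
| PTD 42, 126, 168, 180 | 7.1.3.5 | Ongoing TEAEs | Yes |
| PTD 84 | 7.1.3.4 | Ongoing TEAEs | Yes |
| PTD 270, 365 | 7.1.3.5 (Phase Ib), 7.1.3.6 (Phase Ia Arm A), Table 5 (Phase Ia Arm B) | Ongoing TEAEs | Yes |
| PTD 210, 312 | 7.1.3.5 and table footnotes | Long-term RT toxicity, by phone | No |

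Contacts with the ongoing-TEAE line: 4 + 1 + 2 = 7. All contacts: 7 + 2 = 9.

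**2. Can a new event fit the line?** The TEAE window closes at Day 30 after RT. The earliest of the seven visits is PTD 42 with a window of ±7 days, so no earlier than 42 − 7 = PTD 35. An event that starts after Day 30 is not a TEAE and so cannot be an ongoing TEAE. The AE reporting period continues for a further 365 − 30 = 335 days.

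**3. What does the SAP need?** Of the three routes into late toxicity in SAP 15.2.3, only worsening without a gap plausibly fits an ongoing TEAE. First occurrences and recurrences after a gap are new events, which the visit line leaves out.

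**4. Do the other assessments feed the same output?** SAP 15.2.1 takes its AE frequency tables from the Adverse Events eCRF pages, and the SAP specifies no output for the tissue evaluation. A tissue finding therefore counts as late toxicity only if the site enters it as an AE. The tissue evaluation covers the irradiated field, and the two calls cover RT toxicity, with no other assessments at those contacts. Neither is aimed at late systemic effects of M3814 or cisplatin, and both calls come after the 3-month review.

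**5. What do the general rules require?** Sections 7.4.1.2 and 7.4.1.3 together require new events to be sought and recorded at all nine contacts. So the protocol gives two instructions for the same seven visits, and only the general one covers new events.

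**The case against.** The strongest reply is that the protocol already settles the matter. Section 7.4.1.2 is an explicit rule to ask and record at each visit. Section 7.4 calls for comprehensive toxicity assessment to 12 months after RT, and 7.4.1.7 has AEs recorded continuously. The visit bullets do not contain the word only, whereas the Table 7 footnote for the ancillary part does use it to restrict late AE assessment to local tolerability. Following up ongoing TEAEs is compatible with a separate duty to record new AEs.

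Much of this stands, and it rules out three stronger conclusions that a reader might infer:

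- *That no contact after PTD 30 asks for anything beyond ongoing TEAEs.* The calls at PTD 210 and 312 are for long-term RT toxicity. Section 7.1.3.2 also has a full AE assessment on "PTD 7, 14, 21, 28 and 35 (Phase Ia, Arm B) or on PTD 8, 15, 22 and 37", the second list being for the first three Phase Ib Arm A subjects. Tissue evaluation takes place at all seven clinic visits.
- *That new late toxicity is not solicited, so the SAP outputs have no data source.* Sections 7.4.1.2 and 7.4.1.3 require these events to be collected.
- *That the RP2D is biased.* Nothing in the documents shows how sites read the schedule or how often late events occur. Of the seven visits only PTD 42 and 84 fall within the 3-month follow-up, and both include tissue evaluation.

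What the reply does not remove is the mismatch itself. A site working from the visit schedule meets a defined term that excludes new events, and must go to another section to learn that they are required. The SAP has no check that would show which instruction a site followed.

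**Conclusion.** The point holds as a conflict between two operative instructions, at 7 of the 9 common contacts from PTD 42 to PTD 365. Collection of new late AEs is required by 7.4.1.2 and 7.4.1.3 and partly supported by the tissue evaluation and the two calls. The visit lists and table footnotes, read literally, do not ask for them. The likely direction of error is under-recording of late toxicity.

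The size cannot be stated in events. That would need a late-event rate and the share of sites that follow the schedule literally, and the documents give neither. The conclusion rests on the TEAE definition in 7.4.1.3 being applied as written and on some sites working from the schedule tables, which is plausible but not shown. It merits correction because the affected data are meant to inform escalation and the RP2D and because the correction is simple.

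**What to change.** Reword the follow-up AE footnote in Tables 1 to 6 (footnote j in Tables 1 to 3, i in Table 4, l in Table 5, k in Table 6) and the matching bullets in 7.1.3.4, 7.1.3.5 and 7.1.3.6 to *Assessment of AEs (new and ongoing)*. This agrees with 7.4.1.2 and 7.4.1.3 and matches what SAP 15.2.3 needs, so the SAP itself does not have to change. The visits already take place and no procedure is added. The cost is a wording change and slightly more AE data entry.
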